6.2.9 Clinical Laboratory Tests

Subjects must be fasting (i.e., nothing by mouth for at least 4 hours before the visit; drinking water during the 4-hour fast before clinical laboratory assessments is permitted). All samples (except urine pregnancy tests) will be processed by a central laboratory. The following parameters will be assessed:

Table 11: Clinical Laboratory Tests

Serum Chemistry	Hematology	Additional Tests

 ▪ Glucose ▪ Aspartate aminotransferase (AST) ▪ Alanine aminotransferase (ALT) ▪ Alkaline phosphatase (AP) ▪ Lactate dehydrogenase (LDH) ▪ Sodium ▪ Phosphorus ▪ Potassium ▪ Chloride ▪ Creatine phosphokinase (CPK) ▪ Globulin ▪ Cholesterol (HDL and LDL) ▪ Creatinine ▪ Blood urea nitrogen (BUN) ▪ Prothrombin (PT) and INR (International Normalized Ratio) ▪ Serum calcium ▪ Total bilirubin ▪ Triglyceride ▪ Gamma glutamyl transpeptidase 	
 ▪ Hematocrit ▪ Hemoglobin ▪ Red Blood Cell Count ▪ White Blood Cell Count with Differential ▪ Platelet Count ▪ Mean corpuscular volume ▪ Mean corpuscular hemoglobin ▪ Mean corpuscular hemoglobin concentration 	
 ▪ Serum (at screen visit only) and Urine Pregnancy (WOCBP only)¹ ▪ ²Urine drug screens will test for: 
 amphetamines, barbiturates, cocaine, cannabinoids, opioids, phencyclidine (PCP), and methamphetamines

Serum Chemistry	Hematology	Additional Tests
(GGT) 
 ▪ Serum glutamic pyruvic transaminase (SGPT) ▪ Serum glutamic oxaloacetic transaminase (SGOT) ▪ Uric acid 		

- 1 If positive at any visit during the study, confirm by serum pregnancy test.
- 2 Positive drug screen for phencyclidine (PCP), MDMA (ecstasy), cocaine, and/or methamphetamine(s) is exclusionary. Eligibility of subjects who test positive for cannabinoids is up to the discretion of the investigator.

Clinically significant abnormal values at screening may be repeated to confirm eligibility.

The central laboratory will provide a laboratory manual and appropriate supplies (containers and labels). Laboratory values that are out of range will be identified and may be repeated at the investigator’s discretion with sponsor approval. The investigator will determine if any out-of-range laboratory values that emerge during treatment are clinically significant and if so, record these on the appropriate source document and on the AE CRF page if applicable. All clinically significant out-of-range laboratory values will be followed until they return to normal, or become medically stable.

6.2.10 Twelve-Lead Electrocardiogram

The ECGs will be sent to a central ECG laboratory for interpretation. ECG equipment and an ECG manual will be provided by the central ECG lab.

Any clinically significant abnormality noted by the central reader on the screening ECG will be recorded on the appropriate source document and will result in exclusion of the subject from this study. The investigator may refer the subject for further evaluation and will continue to follow the subject’s condition until the changes have resolved or the subject is medically stable.

6.2.11 Concomitant and Prohibited Medications

Concomitant medications, taken within 30 days of screening and throughout the study, include over the counter medications, topical skin ointments and/or creams, prescription medications, herbal supplements, and/or vitamins. These medications will be recorded on the appropriate source document and on the appropriate CRF at all visits including screening, run-in, and end of study (or early discontinuation) through the duration of the study.

Migraine prophylaxis medications are allowed if subjects have been on a stable dose for at least 30 days prior to screening and with no changes during the study.

Medications with ergot or another Triptan or vasoconstrictor drugs are prohibited on the day of the confirmed migraine prior to M207 application and for 24-hours post-administration of M207.

Aspirin, acetaminophen, NSAIDS, and other PRN or daily medications taken specifically for migraine symptoms are prohibited on the day of a confirmed migraine prior to M207 application and during the two hours following patch application.

On the day of M207 application, subjects will enter into the eDiary whether they took any medications (other than M207) for migraine symptoms prior to M207 application and/or during the 48 hours post M207 application.

Table 12 lists all prohibited concomitant medications taken within 10 days prior to the Run-in Period and for the duration of this study.

Table 12: Prohibited Concomitant Medications

Drug Type	Medication
Monoamine oxidase inhibitors	Selegiline Tranlycypromine Isocarboxazid phenelzine
Selective serotonin reuptake inhibitors (SSRIs)	Paroxetine Fluoxetine Sertraline Citalopram Escitalopram Fluvoxamine
Serotonin-norepinephrine reuptake inhibitors (SNRIs)	Duloxetine Venlafaxine Desvenlafaxine Milnacipran Levomilnacipran
All Prescription Anticoagulants	Pradaxa Coumadin Eliquis Xarelto

6.2.12 Assessment of Adverse Events

AEs are collected from the time of signing the informed consent form and throughout the study duration. New systemic and skin AEs will be recorded on the appropriate source document and CRF.

6.2.13 Subject Reported and Investigator Reported Skin Assessments

Subject reported bruising, bleeding (at 30 minutes only), erythema, edema, skin itching and skin pain are collected through the eDiary and will also be recorded as adverse events in the eCRF. The subject is also provided a Subject Skin Grading Card to help him/her assess whether they have any skin reaction(s) and how to grade any reaction(s) (see [Appendix 4](#)). If the subject contacts the investigator at any time point for worsening or non-resolving reactions, the subject must be seen for an unscheduled visit. The skin reaction(s)/symptom(s) will be assessed, recorded as adverse events in the eCRF and followed to resolution.

In addition, investigator skin assessments in [Section 6.2.13.1](#) will be completed at each in-clinic visit during the treatment period. Any findings related to the upper arm(s) where the patches were applied will be recorded as an adverse event in the eCRF and followed until the signs/symptoms resolve.

6.2.13.1 Investigator Skin Assessments

The following skin assessment will be made by the investigator at each in clinic visit starting at month 1. The entire surface area of the outer upper arm from the upper shoulder to the elbow will be assessed for the following skin signs or symptoms. For further instructions, photographs and descriptors are in [Appendix 5 \(Investigator Assessments - Skin Signs or Symptoms and Photographs\)](#) and [Appendix 6 \(Investigator Assessments – Rating for Bruising, Erythema, Swelling and Photographs\)](#).

Skin signs or symptoms	Indicate arm assessed: Subject's Left and/or Right (circle)
Blisters or pustules?	Present: Yes or No If Yes, describe:
Scaly or flakey skin?	Present: Yes or No If Yes, describe:
Erosions or open sores?	Present: Yes or No If Yes, describe:

Skin signs or symptoms	Indicate arm assessed: Subject's Left and/or Right (circle)
Scarring?	Present: Yes or No If Yes, describe:
Hyperpigmentation or Hypopigmentation?	Present: Yes or No If Yes, describe:

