6.1.3 Day 1 (Visit 3, Dispense Study Medication)

- Perform brief physical exam, including weight
- Record vital signs: temperature, respiratory rate (RR), blood pressure (BP), and heart rate (HR)
- Review run-in eDiary data for subject compliance and eligibility for treatment
- Confirm subject is willing to treat all eDiary-confirmed migraine attacks with study medication, and is willing to consistently perform eDiary completion for up to 12 months
- Record concomitant medications, including medication(s) taken to treat migraine attacks
- Urine pregnancy test for all WOCBP
- Record Adverse events
- Train the subject on how to apply the patch to the upper arm with the applicator and have the subject practice applying the demo patches to his/her arm 2-3 times (more is allowable, if necessary)
- Record that the subject can apply patch(es) with the applicator unaided
- Instruct the subject to apply the patches on the same upper arm for each application
- Reconfirm subject's eligibility based on inclusion/exclusion criteria
- Dispense CTM kit and the applicator
- Provide instructions for scheduling the next visit in one month

- Remind the subject that ergot, another triptan and/or vasoconstrictor drugs are prohibited on the day of patch application prior to applying and within 24-hours post-administration of the patch
- Provide any follow-up eDiary training necessary and re-dispense the eDiary
- Dispense the Subject Skin Grading Card (Appendix 4) and instruct the subject to refer to this card when grading their skin reaction(s)/symptom(s) in the eDiary.

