- Perform Investigator Skin Assessment (presence of blisters, scaly or flakey skin, erosions or open sores, scarring, hyperpigmentation, bruising, redness, and/or swelling) of upper arm where patches have been applied
- Any cutaneous signs or symptoms found on the investigator skin assessment will be recorded as an adverse event on the eCRF and followed to resolution.
- Record concomitant medications
- Record adverse events. In addition, any skin reaction(s) entered into the eDiary by the subject must also be recorded as an adverse event in the eCRF and followed to resolution.

6.1.6 Month 9 (Visit 8) and Month 12 End of Study Final Visit (Visit 9/or Early Termination)

The Month 9 and 12 visits are to be scheduled on (or within ± 7 days) of the protocol specified study day, i.e., on study days 252 (Month 9) and 336 (Month 12). The following procedures will be performed. If a subject terminates early from the study at any time after applying M207, an Early Termination visit must be scheduled to occur within 7-14 days after the subject's last patch application.

- Administer the Migraine Assessment of Current Therapy (Migraine-ACT) to be completed by the subject
- Collect the applicator, any unused patches, and perform accountability
- Dispense M207 patches (Month 9 only)
- Perform physical exam, including weight and height (Month 12 final visit/or early termination only)
- Record vital signs: temperature, respiratory rate (RR), blood pressure (BP), and heart rate (HR)
- Collect blood (4-hr fasting) for clinical laboratory measurements including clinical chemistries and hematology (Month 12 final visit/or early termination only)
- Collect urine for urine pregnancy test for all WOCBP
- Perform 12-lead electrocardiogram (ECG) (Month 12 final visit/or early termination only)
- Ensure subject is dispensed a Subject Skin Grading Card (at Month 9 only)
- Collect and review subject's eDiary data with the subject for the following:
 - Subject compliance with study drug treatment and subject responses in eDiary
- Perform Investigator Skin Assessment (presence of blisters, scaly or flakey skin, erosions or open sores, scarring, hyperpigmentation, bruising, redness, and/or swelling) of upper arm where patches have been applied
- Any cutaneous signs or symptoms found on the investigator skin assessment will be recorded as an adverse event on the eCRF and followed to resolution.
- Record concomitant medications

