6.2.13.3 Other Skin Assessments – Erythema and Edema

Erythema and Edema will be assessed by the investigator at each in clinic visit starting at Month 1.

The following ratings will be used to describe the amount of erythema and edema indicative of irritation:

Symptom	Rating (circle)
Skin Erythema	0 (clear) = None 1 (mild) = $\leq 25\%$ Present in the upper arm region of all M207 applications 2 (moderate) = ≥ 26 to $\leq 50\%$ Present in the upper arm region of all M207 applications 3 (severe) = $> 50\%$ Present in the upper arm region of all M207 applications

Symptom	Rating (circle)
Skin Edema	0 (clear) = None 1 (mild) = $\leq 25\%$ Present in the upper arm region of all M207 applications 2 (moderate) = ≥ 26 to $\leq 50\%$ Present in the upper arm region of all M207 applications 3 (severe) = $> 50\%$ Present in the upper arm region of all M207 applications

Adverse Events of Special Interest: Any site reactions requiring further evaluation or care (e.g., by a dermatologist), as well as those resulting in scarring are considered adverse events of special interest. If these reactions are detected, the de-identified photograph of the patch application site and contralateral arm (containing the date of photograph, visit number and subject number) must be transmitted to the sponsor within 24 hours of the clinic visit for further dermatological evaluation.

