8.2 Adverse Event Definitions

8.2.1 Adverse Events (Adverse Experiences)

Collection of systemic and cutaneous AEs will be initiated after the ICF has been signed and conclude when the post-study procedures are completed (or Early Discontinuation). This includes the time between screening and the first patch application.

An AE is any untoward medical event that occurs in a clinical investigation, where a subject is administered a medicinal (investigational) product or medical device, and which does not necessarily have a causal relationship between the event and the treatment. An AE can be any

unfavorable and unintended sign or symptom, including clinically significant abnormal laboratory result, concomitant illness, or worsening of an existing medical condition.

A Treatment Emergent Adverse Event (TEAE) is an event that emerges during treatment having been absent pre-treatment, or worsens relative to the pre-treatment state.

Abnormal laboratory tests that are clinically significant, as determined by the investigator, should be reported as AEs if:

- the test result is associated with accompanying symptoms;
- the test result requires additional diagnostic testing or medical/surgical intervention;
- the test result leads to discontinuation from the study, significant additional concomitant drug treatment, or other therapy;
- the test result is considered to be an AE by the investigator or sponsor.

Merely repeating an abnormal test, in the absence of any of the above conditions, does not constitute an AE. Any abnormal test result that is determined to be an error does not require reporting as an AE.

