11.2.2. Investigator Skin Assessments

The investigator skin assessment will be made at each in clinic visit starting at month 1. The entire surface area of the outer upper arm from the upper shoulder to the elbow will be assessed for the following skin signs or symptoms.

Investigator reported skin bruising, skin redness (erythema), and skin swelling (edema) at the application site will be collected and will also be recorded in the eCRF.

The amount of bruising, erythema, and edema and the presence of skin signs and symptoms will be categorized and assessed as follows:

Skin signs or symptoms	Indicate arm assessed: Subject's Left and/or Right (circle)
Blisters or pustules?	Present: Yes or No If Yes, describe:
Scaly or flakey skin?	Present: Yes or No If Yes, describe:
Erosions or open sores?	Present: Yes or No If Yes, describe:
Scarring?	Present: Yes or No If Yes, describe:
Hyperpigmentation or Hypopigmentation?	Present: Yes or No If Yes, describe:

Bruising assessments (visual rating) will be performed using the following ratings:

Symptom	Rating (circle)
M207 application sites have bruising spots?	0 (clear) = None 1 (mild) = ≤ 25% Present in the upper arm region of all M207 applications 2 (moderate) = ≥ 26 to ≤ 50% Present in the upper arm region of all M207 applications 3 (severe) = > 50% Present in the upper arm region of all M207 applications

Erythema Severity Categories:

Symptom	Rating (circle)
Skin Erythema	0 (clear) = None 1 (mild) = ≤ 25% Present in the upper arm region of all M207 applications 2 (moderate) = ≥ 26 to ≤ 50% Present in the upper arm region of all M207 applications 3 (severe) = > 50% Present in the upper arm region of all M207 applications

Edema Severity Categories:

Symptom	Rating (circle)
Skin Edema	0 (clear) = None 1 (mild) = ≤ 25% Present in the upper arm region of all M207

	
applications
 
2 (moderate) = ≥ 26 to $\leq 50\%$ Present in the upper arm region of all M207 applications
 
3 (severe) = $> 50\%$ Present in the upper arm region of all M207 applications

--	---

The frequencies of amount of bruising, erythema, and edema at the application site as assessed by the Investigator at Months 1, 2, 3, 6, 9, 12, and at the 2-week post-study visit will be summarized. The proportion of subjects with any amount of all 3 symptoms (erythema, edema, and bruising) and all combinations of the 3 symptoms will be summarized by time point.

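### The investigator skin form has no pre-dose baseline, so old scars and pigment marks enter the by-visit skin tables and may be misclassified as treatment-emergent

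*Protocol*

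**What the plan says.** **Timing.** Protocol 6.2.13.1 says "The following skin assessment will be made by the investigator at each in clinic visit starting at month 1", and SAP 11.2.2 agrees: "The investigator skin assessment will be made at each in clinic visit starting at month 1". Protocol Table 10, SAP Table 1 and Protocol Appendices 5 and 6 show the same start. Nothing arm-specific, neither form nor photograph, is scheduled at Visits 1 to 3.

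**Area.** "The entire surface area of the outer upper arm from the upper shoulder to the elbow will be assessed" (Protocol 6.2.13.1). This is wider than the patch sites.

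**Recording.** Protocol 6.1.5, repeated in 6.1.6 and 6.1.8, says: "Any cutaneous signs or symptoms found on the investigator skin assessment will be recorded as an adverse event on the eCRF". Appendix 5 has the same rule, and Appendix 6 applies it to every bruising, erythema or edema rating of 1 or more. Section 6.2.13 limits it to the arm or arms where patches were applied. None of these exempts a mark that was already there.

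**Analysis.** Protocol 7.1.1, SAP 4.2 and SAP 11.2.2 summarise the proportion of subjects with skin signs present, and the frequency of each bruising, erythema and edema grade, at Months 1, 2, 3, 6, 9, 12 and the post-study visit.

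**Definitions.** Under Protocol 8.2.1 a TEAE "is an event that emerges during treatment having been absent pre-treatment, or worsens relative to the pre-treatment state". Under 6.2.13.3, site reactions that need further evaluation or care, "as well as those resulting in scarring are considered adverse events of special interest".

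**Pre-dose skin data.** Physical exams take place at screening and on Day 1, the latter described as "Perform brief physical exam, including weight". A footnote to Table 10 lists a dermatologic component for the physical exam.

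**The concern.** Protocol 1.3 gives the effect of repeated application as the reason for the study. Scarring and lasting pigment change are the skin outcomes for which a 6- to 12-month study adds most to the earlier single-attack trial. They are also the signs on the form that an adult may already carry on the upper arm, from old injury, vaccination or sun.

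A TEAE is defined against the pre-treatment state, but the form that finds these marks is never completed before treatment. There is one arm, so no control group shows the background. If old marks are counted with new ones, the reported rates of scarring and pigment change overstate the product's effect by an unknown amount. A baseline that was not recorded cannot be fully recovered later.

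**Working it through.** The plan states no figure on this point, and SAP 3.5 says the sample size has no statistical basis. The check is therefore mainly a comparison of sections.

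**1. Is there a structured baseline?** No. Every description of the investigator skin form starts at Month 1 (Day 28 ± 7).

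**2. Do the by-visit tables separate old from new?** No. In the same endpoint list (Protocol 7.1.1), physical examination, vital signs, laboratory tests and ECG are changes or shifts from baseline. The investigator skin endpoints are presence or amount at each visit. A scar from childhood is a Yes at every visit. This holds even if every AE is classified correctly.

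**3. Can an old mark become a TEAE?** Yes, though not by definition.
- The visit sections make any finding an AE. Section 6.2.12 speaks of new AEs, and 8.2.1 requires absence before treatment or worsening.
- SAP 6.3, written for incomplete start dates, first takes the eCRF occurrence type where given. It then treats an event occurring on or after the first dose as treatment-emergent.
- Both routes depend on someone knowing when the mark arose. A mark first noted at Month 1 and dated then becomes a TEAE.

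**4. Do other data fill the gap?** Partly.
- The pre-dose physical exams are general, and the Day 1 exam is brief. SAP 11.6 only lists exam findings and does not link them to the arm assessment.
- Exclusion criterion 10 concerns planned activities that affect the site. It does not exclude existing scars or pigment change.
- Appendix 5 asks for the size, colour and shape of scars, and whether scars and pigment change stay within the application area. This helps with a mark clearly outside that area, less with a small mark inside it.
- Causality is rated for each AE, but Protocol 8.2.1.4 handles an unknown cause as related for reporting purposes.

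**5. Illustration of size.** Inputs: N = 250 (Protocol 3.2.1). The prevalence p of an existing scar or pigment mark and the true new incidence i are assumptions; the documents give neither.

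Subjects with an existing mark = N × p:

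| p | N × p |
|---|---|
| 2% | 5 |
| 5% | 12.5 |
| 10% | 25 |
| 20% | 50 |
| 30% | 75 |

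Without a baseline, the proportion with a mark is p + (1 − p) × i. With i = 1%, truly new marks affect 250 × 0.01 = 2.5 subjects.
- p = 2%: 0.02 + 0.98 × 0.01 = 0.0298, or about 7.5 subjects. Share with an existing mark: 0.02 / 0.0298 = 67%.
- p = 30%: 0.30 + 0.70 × 0.01 = 0.307, or about 77 subjects. Share: 0.30 / 0.307 = 98%.

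The chance that at least one of 250 subjects has an existing mark at p = 2% is 1 − 0.98^250 = 99.4%.

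**The case against.** The strongest reply is that the definitions already exclude old marks. A reader might infer that the plan makes existing marks TEAEs. It does not. The visit sections say AE, not TEAE; 8.2.1 excludes a mark known to predate treatment; SAP 11.2 puts only TEAEs in the AE summary tables. What remains is a risk of misclassification, because the information those definitions need is not collected systematically.

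A reader might also infer that every old scar becomes an AE of special interest. The definition in 6.2.13.3 requires a site reaction, so a vaccination scar does not qualify, though one of uncertain origin could be mistaken for such an event. That section also asks for photographs of the application site and the other arm. These are taken only once such an event is detected, and 6.1.4 lets patches go on the other arm, so that arm is not always an untreated comparator.

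A third inference is that old and new marks could never be told apart. That goes too far. The dermatologic exams, medical history, Appendix 5 descriptions and causality ratings allow partial separation in individual subjects. They do not correct the by-visit tables, which use none of them.

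Finally, it may be said that the graded ratings cannot be used before dosing, because 6.2.13.2 and 6.2.13.3 refer to the region of all M207 applications. Appendix 6 answers this by making the entire outer arm, shoulder to elbow, the denominator. It is true, however, that the Yes/No signs in 6.2.13.1 have no grade, so a rule based on a lower grade cannot be used for scarring or pigment change.

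**Conclusion.** The point holds in a limited form. As planned, the by-visit tables of investigator skin signs count marks that predate treatment together with new ones. Separately, such marks may be misclassified as TEAEs when first noted and dated after dosing. The documents do not support saying that they will be so classified, or that old scars are AEs of special interest.

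The size is unknown. The 5 to 75 of 250 subjects rests wholly on an assumed prevalence of 2% to 30%, and the 67% to 98% share also on an assumed new incidence of 1%. These counts describe subjects carrying an existing mark. They apply to the presence tables if every such mark is seen, and are not an estimate of false TEAEs, since some marks will be recognised as old. The qualitative conclusion does not depend on the prevalence: no baseline column exists, and there is no control arm. The change is cheap and should be made; the gap does not invalidate the trial.

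**What to change.** 1. **Add a baseline.** Complete the existing 6.2.13.1 to 6.2.13.3 form for both upper arms at the screening physical exam, with the whole-outer-arm denominator of Appendix 6. It must precede any demo patch: demo training starts at Visit 2 (6.1.2.1), which may be combined with Visit 1, so Day 1 is too late for a clean record.
2. **Change the tables.** In SAP 11.2.2, tabulate Yes/No signs as newly present against baseline, or worsened according to the Appendix 5 description. Tabulate bruising, erythema and edema as shifts from baseline grade.
3. **State the rule.** Add to the SAP that an unchanged baseline skin finding is not a TEAE.
4. **Reconcile the recording rules.** Bring Protocol 6.1.5, 6.1.6, 6.1.8, 6.2.13 and Appendices 5 and 6 into line with the reference to new AEs in 6.2.12 and the TEAE definition in 8.2.1.
5. **Subjects already treated.** Use the pre-dose dermatologic exam record and the Appendix 5 descriptors, and disclose in the report that no structured baseline exists for them.

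The cost is a few minutes per subject at a visit that already includes a physical exam, a short protocol amendment and a modest change to the SAP tables. No extra visit or staff is needed.
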